**Table 2: Analysis Windows for Unscheduled and Early Termination Visits**

	Nominal Visit	Safety Analyses			Efficacy Analyses		
		Lower	Target	Upper	Lower	Target	Upper
Part A, Period 1	Screening	-28	-1	-1	-28	-1	-1
	Visit 2-Randomization	1	1	1	1	1	1
	Visit 3-Week 2	2	15	22	12	15	18
	Visit 4-Week 4	23	29	43	26	29	32
	Visit 5-Week 8	44	57	71	54	57	60
	Visit 6-Week 12	72	85	99	82	85	88
	Visit 7-Week 16	100	113	127	110	113	116
	Visit 8-Week 20	128	141	155	138	141	144
Part A, Period 2	Visit 9-Week 24	156	169	183	166	169	172
	Visit 10-Week 28 (PAP2 Week 4)	184	197	211	194	197	200
	Visit 11-Week 32 (PAP2 Week 8)	212	225	239	222	225	228
	Visit 12-Week 36 (PAP2 Week 12)	240	253	267	250	253	256
	Visit 13-Week 40 (PAP2 Week 16)	268	281	295	278	281	284
	Visit 14-Week 44 (PAP2 Week 20)	296	309	323	306	309	312
	Visit 15-Week 48 (PAP2 Week 24)	324	337	351	334	337	340
Part B	Visit B1-Day 1	1	1	1	1	1	1
	Visit B2-Week 2	2	15	22	12	15	18
	Visit B3-Week 4	23	29	43	26	29	32
	Visit B4-Week 8	44	57	71	54	57	60
	Visit B5-Week 12	72	85	99	82	85	88
	Visit B6-Week 16	100	113	127	110	113	116
	Visit B7-Week 20	128	141	155	138	141	144
	Visit B8-Week 24	156	169	183	166	169	172

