Event	Day -28 to Day -1 (Visit 1)	Randomization ^{1, 2} Day 1 (Visit 2)	Week 2 (Visit 3)	Week 4, 8 (Visit 4, 5)	Week 12 (Visit 6)	Week 16, 20 (Visit 7, 8)	Week 243,4 (Visit 9)	Week 28 ⁵ (Visit 10)	Week 32 (Visit 11)	Week 36 (Visit 12)	Week 40, 44 (Visit 13, 14)	Week 484 (Visit 15)	Safety Follow-Up Visit
Informed consent	X												
Eligibility assessment	X	X											
Demographics	X												
Medical history	X	X											
Randomization		X					X^7						
PE	X	X					X					Х	X
Brief PE				X	X	X			X	X	Х		
Height	X												
Weight	X	X		X	X	X	X		X	X	X	X	X
Pregnancy test ⁸	X	X ⁹		X	X	X	X	X	X	X	X	X	
Tuberculosis test	X												
Clinical laboratory testing ¹⁰ , 11	X ¹²	X	X	X	X	X	X	X	X	X	X	X	X
Lipid assessment ¹³		X			X		X			X		X	X
HBV and HCV test	Х												
12-lead electrocardiogram	Х	X			Х		X			X		Х	X
Vital signs	X	X		X	X	X	X		X	X	Х	X	X
SALT assessment	Х	X		X	X	X	X	X^{14}	X^{14}	X^{14}	X14	Х	
Photographs	X	X		X	X	X	X	X	X	X	Х	X	
SPRO and QPRO		X			X	X	X						
CGI-S and PGI-S		X			Х	X	X						
CGI-I and PGI-I					X	X	X						
Dispense study drug		X		X	X	X	X^7	X^{15}	X^{15}	X^{15}	X15		
Pharmacokinetic blood sampling ¹⁶		X			X		X						
Study drug accountability				X	X	X	X		X	X	X	X	_
Adverse events	X				X					X			X
Concomitant medications	X		X			X				X			

PE = Physical Examination; HBV= hepatitis B virus; HCV = hepatitis C virus; SPRO = Satisfaction of Hair Patient Reported Outcome; QPRO = Quality of Hair Patient Reported Outcome; CGI-S = Clinical Global Impression of Severity; CGI-I = Clinical Global Impression of Improvement; PGI-S= Patient Global Impression of Improvement; PGI-I = Patient Global Impression of Improvement;

- ¹ Day 1 (Visit 2) may occur any time after Screening laboratory results are available and reviewed by the Investigator.
- ² For Part A, Period 1, all subsequent visits and week increments should be based on the date of Visit 2. All visit windows are ± 2 days.
- ³ Week 24 from Part A, Period 1 will also serve as the Day 1 visit for Part A, Period 2 for those who meet criteria to continue into the Dose Modification Phase.
- ⁴ Also serves as the Early Termination Visit for patient withdrawal in this period.
- ⁵ For Part A, Period 2, all subsequent visits and week increments should be based on the date of Week 24 (Visit 9). All visit windows are ±2 days.

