#### 8.1.2. Assessment Time Windows

The visit schedule for all study assessments is provided in Appendix 15.2, by Part. For scheduled visits, there will be no reassignment of the analysis visit based on date. Unscheduled visits and early termination visits will be reassigned based on the analysis windows in the below table and the schedule of events. Assessments in part B will be windowed counting from the part B treatment start date. Assessments may only be re-assigned to visits where they were to be collected per the schedule of events. The latest assessment in a window will be selected as the visit used in summaries, unless otherwise specified. All visits will be included in by-patient data listings.

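### SAP Table 2 keeps the Week 24 safety window open to Day 183, so unscheduled safety values from about the first two weeks of Period 2 are labelled Week 24

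*SAP*

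**What the plan says.** **Which values are windowed.** SAP 8.1.2: "Unscheduled visits and early termination visits will be reassigned based on the analysis windows in the below table and the schedule of events". Planned visits are exempt: "For scheduled visits, there will be no reassignment of the analysis visit based on date". An assessment can be moved only to a visit at which the schedule calls for it.

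**Which value is used.** SAP 8.1.2: "The latest assessment in a window will be selected as the visit used in summaries, unless otherwise specified". For PCS laboratory values, SAP 9.5 takes the highest CTCAE grade in the window instead.

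**The windows.** In SAP Table 2 the row "Visit 9-Week 24" has a safety window of Days 156 to 183 (target 169) and an efficacy window of Days 166 to 172. The row "Visit 10-Week 28 (PAP2 Week 4" has a safety window of Days 184 to 211 (target 197).

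**The day count.** SAP 8.1.2 restarts it for the re-treatment phase only: "Assessments in part B will be windowed counting from the part B treatment start date". It has no such sentence for Period 2.

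**When Period 2 starts.** Protocol Table 1, footnote 3: "Week 24 from Part A, Period 1 will also serve as the Day 1 visit for Part A, Period 2". Footnote 7 has Period 2 drug dispensed at that visit, and Protocol 10.1 has the first dose of each phase taken in the clinic on Day 1. Footnote 5 dates the later visits from the actual Visit 9 date: "For Part A, Period 2, all subsequent visits and week increments should be based on the date of Week 24 (Visit 9", with ±2 days allowed.

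**The concern.** For a responder, the Week 24 visit is the last day on the Period 1 dose and the first day on a reduced dose or placebo. A window that stays open to Day 183 mixes values from before and after that change under one visit label. No sentence in the SAP closes it at re-randomization.

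The SAP treats comparable cases differently. Part B windows restart at the treatment change. SAP 9.3 divides treatment-emergent adverse events by the first dose in each Part/Period. So an adverse event on Period 2 Day 10 belongs to Period 2, while an unscheduled laboratory value from the same day is labelled Week 24.

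Two results are at stake. The scheduled Week 24 laboratory, lipid, vital-sign or ECG value can be displaced by a later one taken on different treatment. And a PCS laboratory value that first arises after the switch can be filed at Week 24. The Part A laboratory mean-change and PCS tables are marked in SAP Appendix 15.4 for the abbreviated report. With about 25 patients per Period 2 arm (Protocol 13.1), a single misplaced value would be visible.

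**Working it through.** **Step 1: reproduce Table 2.** Target day = 7 × week + 1, counted from Period 1 Day 1. Safety upper bound = midpoint to the next target. Safety lower bound = previous upper bound + 1. Efficacy window = target ± 3.

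- Week 24 target: 7 × 24 + 1 = 169. Week 28 target: 7 × 28 + 1 = 197.
- Week 20 upper bound: (141 + 169)/2 = 155, so Week 24 opens at Day 156.
- Week 24 upper bound: (169 + 197)/2 = 183, so Week 28 opens at Day 184.
- Week 24 efficacy window: 166 to 172.

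The safety rule returns all 13 Part A rows from Week 2 to Week 48 exactly. The efficacy rule was checked at Weeks 24, 28 and 48 and matched. The SAP does not state the anchor in words, but the Period 2 day numbers fit a continuous count from Period 1 Day 1.

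**Step 2: post-switch days inside the Week 24 window.** Safety overlap = 183 − Visit 9 day; efficacy overlap = 172 − Visit 9 day.

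| Visit 9 on Day | Safety overlap (days) | Efficacy overlap (days) |
|---|---|---|
| 167 (−2) | 16 | 5 |
| 169 (target) | 14 | 3 |
| 171 (+2) | 12 | 1 |

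At target, the 14 days are Days 170 to 183, that is Period 2 Days 2 to 15.

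**Step 3: a likely source of such values.** Protocol 10.2.1 asks for hematology results to be confirmed at an unscheduled visit within 72 hours before a dose interruption. A repeat up to 3 days after Visit 9 falls inside the Week 24 window if Visit 9 day + 3 ≤ 183, so for any Visit 9 up to Day 180. Samples go to a central laboratory (Protocol 11.10) and Period 2 drug is dispensed at the visit, so such a repeat would ordinarily follow the switch.

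**Step 4: the opposite error.** If Visit 9 slips past Day 183 (Day 190, say, as an assumed delay), unscheduled values from Day 184 until the switch are still on the Period 1 dose but are labelled Period 2 Week 4.

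**Step 5: windows counted from Period 2 Day 1.** The same midpoint rule gives these safety windows:

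| Period 2 visit | Lower | Target | Upper |
|---|---|---|---|
| Week 4 | 2 | 29 | 43 |
| Week 8 | 44 | 57 | 71 |
| Week 12 | 72 | 85 | 99 |
| Week 16 | 100 | 113 | 127 |
| Week 20 | 128 | 141 | 155 |
| Week 24 | 156 | 169 | 183 |

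From Week 8 on these equal the Part B rows. Week 4 opens at Day 2 because Period 2 has no Week 2 visit. With Visit 9 on Day 169, Week 4 covers Days 170 to 211, and the 14 days leave the Week 24 window.

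**The case against.** The best case against is that the reach is small, and most of that stands.

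- **Scheduled visits.** A reader might infer that on-schedule Period 2 visits drop out of their windows, since ±2 days at Visit 9 plus ±2 days at a later visit makes 4, against an efficacy window of ±3. They do not: SAP 8.1.2 never moves a scheduled visit by date.
- **Baseline.** A reader might infer that Period 2 baseline is contaminated. SAP section 4 defines it as the last observation on or before the day of dosing in Period 2, so a later draw cannot enter it.
- **Wrong treatment.** Table 2 assigns a visit label. The PCS tables are titled by Part/Period, and the SAP does not say whether laboratory values are allotted to a Period by date before windowing. Misattribution between treatments is therefore possible but not demonstrated.
- **On-treatment restriction.** SAP 9.5 limits laboratory change from baseline to values on or before last dose. Read as last dose of the Period, this would drop post-switch values from the Period 1 change tables. It does not say so, is not stated for PCS values, and would not place the values under Period 2.
- **The 72-hour repeat.** It applies to hematology values that would lead to interruption, not to any abnormal Week 24 count, and it need not land in the Week 24 window: with Visit 9 on Day 182, a Day 184 repeat falls in Week 28.
- **Other protection.** Clinically significant laboratory results are also recorded as adverse events (Protocol 11.10), and all visits are listed.

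The text of Table 2 as read sets the Period 2 label beside the Visit 9 row, perhaps a layout effect. Either way the value is labelled Week 24 and not as a Period 2 post-baseline visit.

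None of this closes the window. The written rule still lets a post-switch value replace the Week 24 result.

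**Conclusion.** The point holds within limits. Table 2 labels unscheduled and early-termination safety values from the first 14 days of Period 2 as Week 24, or 12 to 16 days within the visit window. Such a value can displace the scheduled Week 24 result, and a post-switch PCS laboratory value can be filed there. This rests on the day count inferred from Table 2 and on Period 2 dosing starting at Visit 9.

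The primary SALT analysis uses the last SALT value in Period 2 and time to LOM uses dates, so neither is materially affected. The efficacy overlap is 1 to 5 days, and unscheduled visits are meant for safety follow-up.

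The 14 days are 14/27 = 52% of the days between the Week 24 and Week 28 targets and 14/168 = 8.3% of a full Period 2. A reader might take these as shares of the data; they are shares of the calendar only. The documents give no frequency of unscheduled visits. About 100 expected responders (50 per dose group) come under the rule; the other 200 or so of the 300 planned patients do not enter Period 2.

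The SAP should be corrected because a stated rule gives a wrong visit label and the remedy is simple.

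**What to change.** In SAP 8.1.2 and Table 2:

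1. Add a sentence that Period 2 assessments are windowed from the Period 2 treatment start date, as is done for Part B.
2. Replace the six Period 2 rows: Week 4 safety window Days 2 to 43, target 29; Weeks 8 to 24 as in the Part B rows. Efficacy windows stay at target ± 3.
3. For re-randomized patients, close the Visit 9 window at Period 2 start and use only values taken before the first Period 2 dose.

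The cost is six rows, a condition on the Visit 9 row, the 8.1.2 text and one programming anchor. No new data are needed and no study procedure changes. It is best done before the database freeze for the abbreviated report.

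The gain is limited. Early Period 2 hematology and chemistry draws would move to Week 4, but the scheduled Week 28 value would usually still displace them in by-visit means. Lipids, vital signs and ECG are not scheduled at Week 28 in Protocol Table 1, so their early values would appear in listings only. What improves is that the Week 24 value is uncontaminated and PCS laboratory values are attributed to the correct Period.

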### **8.1.3. Timing of Analyses**

All final, planned analyses will be performed after the last patient has completed all study assessments in Part B, all relevant study data have been processed and integrated into the analysis database, and the database has been locked. Analyses for the abbreviated report for the NDA, focused on the primary efficacy for Part A and a safety analysis for Part A, will be performed after the last patient completes Part A and the database is frozen. PK analyses and the interim analysis (safety data for Part A Period 1) will be performed after the last patient completes Part A Period 1 and the database is frozen.

Any post hoc, exploratory analyses completed to support planned study analysis, which were not identified in this SAP, will be documented and reported in appendices to the applicable study reports. Any results from these unplanned analyses (post hoc) will also be clearly identified in the text of the applicable study reports.

### **8.1.4. Multiple Comparisons/Multiplicity**

There will be no adjustment for multiple treatment group comparisons in this Phase 2 study.

## **8.2. Primary Endpoints**

### Part A:

This study is designed to be exploratory and descriptive in nature and no formal hypothesis testing is planned. Therefore, descriptive statistics will be used to summarize the results regarding dose modification following successful hair regrowth for each dose group. In Part A, Period 1, a Responder is defined as having an absolute SALT score  $\leq 20$  at Week 24 of the Treatment Period. Only Responders will enter into Part A, Period 2 (Dose Modification) for the primary efficacy analysis. For Part A of the study, there are two co-primary efficacy endpoints. The first co-primary efficacy endpoint is the percentage of patients achieving LOM criteria (SALT  $> 20$ ) compared to the percentage of patients maintaining treatment success (SALT  $\leq 20$ ) for each of the following dose reduction conditions (Period 2 ONLY):

- 12 mg BID reduced to 8 mg BID
- 8 mg BID reduced to 4 mg BID

The second co-primary efficacy analysis is the percentage of patients achieving LOM criteria compared to the percentage of patients maintaining treatment success for each of the following drug discontinuation conditions (Period 2 ONLY):

- 12 mg BID to Placebo
- 8 mg BID to Placebo

### Part B:

For Part B of the study, the primary efficacy endpoint is the percentage of patients by dose group achieving ROR, defined as an absolute SALT score of  $\leq 20$  at Week 24 of re-treatment. The following treatment sequences will be compared:

- Dose reduction in Period 2
  - 12 mg BID reduced to 8 mg BID increased to 12 mg BID
  - 8 mg BID reduced to 4 mg BID increased to 8 mg BID

- Drug discontinuation in Period 2
  - 12 mg BID to placebo to 12 mg BID
  - 8 mg BID to placebo to 8 mg BID

### **8.2.1. Computation of the Primary Endpoints**

The SALT is a measure of hair loss that quantifies the amount of scalp surface without hair in a pre-specified quadrant of the scalp (right side, top, left side, back), that is further summed after applying a quadrant-specific multiplier indicative of scalp surface area contribution, to provide an overall score of total hair loss. An example of the SALT assessment can be found in Appendix 18.2 of protocol.

The primary endpoints for each Part of the study consist of deriving and categorizing the individual overall SALT scores ( $\leq 20$  versus  $> 20$ ).

Due to the variable time on study for each patient within Part A Period 2, the primary analysis visit will be the End of Part A Period 2, where the last observed non-missing SALT value is selected for each patient. Otherwise, missing data will not be imputed for this descriptive, exploratory study.

Patterns of missing values across visits will be listed and summarized with numbers and percentages by treatment and visit.

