Patients in Part A, Period 2 will stay on their assigned dose for a maximum of 24 weeks or until they meet the criteria for loss of regrowth maintenance (LOM), defined as an absolute SALT score >20. Any patient meeting the LOM criteria at any assessment timepoint during Part A, Period 2 will enter Part B of the study and return to their original CTP-543 treatment from Part A, Period 1 (8 mg BID or 12 mg BID). Patients not meeting the LOM criteria (e.g., their absolute SALT score remains \leq 20) at the end of 24 weeks will have the opportunity to continue receiving treatment in the Open-Label Extension study (CP543.5001) or they will complete treatment at Week 24 and return in 4 weeks for the Post-Treatment Safety Follow-up.

Assessment of treatment response using SALT for efficacy will occur at 4, 8, 12, 16, 20 and 24 weeks. The primary efficacy analysis will be conducted when all patients have completed Week 24 of Part A, Period 2. The study design is depicted below.

Part A: Treatment and Dose Modification Phase

Part B: Re-Treatment Phase

Part B: Re-

Figure 2: CP543.2004 Study Design

LOM: Loss of Maintenance

Part B (Re-Treatment Phase)

Any patient from Part A, Period 2 meeting the LOM criteria (SALT > 20) will enter into Part B of the study and return to their original 8 mg BID or 12 mg BID dose assigned in Part A, Period 1. Patients will stay on their assigned dose for 24 weeks regardless of whether they meet the criteria for Restoration of Regrowth (ROR) or not. ROR is defined as the patient's attainment of an absolute SALT score ≤20. Assessment of treatment response using SALT for efficacy will occur monthly during the 24-week period. Patients will have the opportunity to continue receiving treatment in the Open-Label Extension study (CP543.5001) or they will complete treatment at Week 24 and return in 4 weeks for the Post-Treatment Safety Follow-up.

Safety

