scalp hair represented treatment success. Adult and adolescent AA patients participating in the study perceived that, short of 100% scalp hair, the presence of \sim 70-90% scalp hair (median 80%) represented treatment success. Nearly all queried clinicians and patients in this study agreed that for patients with \geq 50% scalp hair loss, successful treatment would be hair regrowth resulting in \leq 20% scalp hair loss.

Therefore, based on the efficacy and safety data observed in the CP543.2001, CP543.2002, and CP543.2003 studies, 8 mg BID and 12 mg BID of CTP-543 will be assessed further for efficacy and safety in this study in patients with moderate to severe alopecia areata. This study will employ SALT as the hair loss assessment tool and the criteria for definition of a responder will be the achievement of an absolute SALT score \leq 20 at Week 24, as this represents a clinically-meaningful treatment success for patients with AA.

For Part A, Period 1 the primary efficacy endpoint will be the proportion of patients who achieve an absolute SALT score of ≤20 at Week 24. This endpoint was chosen based on the data obtained from Study CP543.2001. Choosing this endpoint for Part A, Period 1 will yield an adequate number of patients moving onto the dose modification phase of the study.

For Part A, Period 2 the primary analysis is the proportion of patients who maintain an absolute SALT score of ≤20 at Week 24 following either dose reduction or drug discontinuation. Patients in Part A, Period 2 will stay on the assigned dose for a maximum of 24 weeks or until they meet the criteria for LOM. The criteria for LOM is an absolute SALT score >20. This criteria will reflect a clear loss of maintenance of the hair regrown in Period 1 but without a major loss of hair which would be emotionally disturbing to the patient.

For Part B the primary analysis is the proportion of subjects who achieve an absolute SALT score of ≤20 at Week 24 after re-treatment. Any patient from Part A, Period 2 meeting the LOM criteria will enter into Part B of the study and return to their original 8 mg BID or 12 mg BID dose from Part A, Period 1. Patients will stay on their assigned dose for 24 weeks.

Table 1: Schedule of Assessments: Part A

	Screening	Part A, Period 1					Part A, Period 2				Safety Follow-Up ⁶		

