13.2. Endpoints

13.2.1. Efficacy

Part A (Treatment and Dose Modification Phase) Efficacy Analysis

This study is designed to be exploratory and descriptive in nature and no formal hypothesis testing is planned. Therefore, descriptive statistics will be used to summarize the results regarding dose modification following successful hair regrowth for each dose group. In Part A, Period 1, a Responder is defined as having an absolute SALT score ≤20 at Week 24 of the Treatment Period. Only Responders will enter into Part A, Period 2 (Dose Modification) for the primary efficacy analysis.

The first co-primary efficacy analysis will be the percentage of patients achieving LOM criteria (SALT > 20) compared to the percentage of patients maintaining treatment success (SALT \leq 20) for each of the following *dose reduction* conditions (Period 2 ONLY):

- 12 mg BID reduced to 8 mg BID
- 8 mg BID reduced to 4 mg BID

The second co-primary efficacy analysis will be the percentage of patients achieving LOM criteria compared to the percentage of patients maintaining treatment success for each of the following *drug discontinuation* conditions (Period 2 ONLY):

- 12 mg BID to Placebo
- 8 mg BID to Placebo

Secondary Endpoints for Part A

- Percentage of patients achieving LOM criteria for each *dose reduction* condition at Weeks 4, 8, 12, 16, 20, and 24 (Period 2 ONLY)
- Percentage of patients achieving LOM criteria for each *drug discontinuation* condition at Weeks 4, 8, 12, 16, 20, and 24 (Period 2 ONLY)

- Percentage of responders (defined as "satisfied" or "very satisfied") on the Hair Satisfaction Patient Reported Outcome (SPRO) scale at Weeks 12, 16, 20, and 24 (Period 1 ONLY)
- Percentage of patients achieving an absolute SALT score ≤20 at Weeks 8, 12, 16, 20, and 24 (Period 1 ONLY)
- Relative change in SALT scores from Baseline at Weeks 4, 8, 12, 16, 20, and 24 (Period 1 ONLY)
- Percentage of responders (defined as "much improved" or "very much improved") using the CGI-I at Weeks 12, 16, 20, and 24 (Period 1 ONLY)
- Percentage of responders (defined as "much improved" or "very much improved") using the PGI-I at Weeks 12, 16, 20, and 24 (Period 1 ONLY)
- Change from Baseline in the CGI-S at Weeks 12, 16, 20, and 24 (Period 1 ONLY)
- Change from Baseline in the PGI-S at Weeks 12, 16, 20, and 24 (Period 1 ONLY)
- Change from Baseline on the individual items of the Hair Quality Patient Reported Outcome (QPRO) scale at Weeks 12, 16, 20, and 24 (Period 1 ONLY)

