## 8.5. Other Endpoints

### 8.5.1. Time to First LOM (Part A only)

Time to first LOM (in weeks) will be summarized descriptively with Kaplan-Meier methodology for patients in the Efficacy Population who entered Part A Period 2. Treatment sequence across Period 1 and Period 2 (8 mg BID to 4 mg BID, 8 mg BID to placebo, 12 mg BID to 8 mg BID, and 12 mg BID to placebo) will be used as strata to present quantiles (25%, median, 75%), if estimable. Ninety-five percent confidence intervals for the median will be presented, if estimable, using the Brookmeyer and Crowley (1982) method. If KM statistics are not estimable, standard descriptive statistics for non-censored patients will be displayed.

First LOM is defined as the first date where a patient has an absolute SALT score  $>20$  in Part A Period 2. Time in weeks will be calculated from the date of randomization in Part A Period 2, as

- (date of first LOM (or censored date) - date of Part A Period 2 randomization + 1)/7

Patients who do not experience LOM before completion of Part A Period 2 or otherwise prematurely discontinue from Part A Period 2 will be censored at their last study visit date where SALT was measured in Part A Period 2 of the study, or a maximum of 24 weeks.

A Kaplan-Meier plot over time will also be presented.

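### The Period 2 co-primary uses the last SALT at any Period 2 visit, so patients last seen early with SALT ≤20 and no later reading count as maintained

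*SAP*

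**What the plan says.** - **SAP 8.2.1** gives the analysis value for the Period 2 co-primaries. It sets an end-of-period analysis visit, "where the last observed non-missing SALT value is selected for each patient". That value is classed as ≤20 or >20. The reason given is that time on study varies in Period 2. Otherwise missing data are not imputed.
- **Protocol 8.4** states that for Period 2 "the primary analysis is the proportion of patients who maintain an absolute SALT score of ≤20 at Week 24".
- **Protocol 13.2.1**, where the co-primaries are defined, names no week: "The first co-primary efficacy analysis will be the percentage of patients achieving LOM criteria" is set against the percentage maintaining SALT ≤20. The protocol synopsis and SAP 8.2 also name no week.
- **Protocol 8.1** explains why follow-up varies: "Patients in Part A, Period 2 will stay on their assigned dose for a maximum of 24 weeks or until they meet the criteria". The criteria meant are those of LOM.
- **SAP 8.5.1** handles patients without LOM, in the time-to-LOM analysis, by censoring: they "will be censored at their last study visit date where SALT was measured in Part A Period 2", capped at 24 weeks.
- **SAP 8.2.3** plans no sensitivity analysis of the primary. **SAP 13** does not list the last-observed rule as a change. **Protocol 13.4.3** leaves missing SALT data to the SAP, and **SAP 2** gives the SAP primacy where the two differ.

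**The concern.** Varying time on study justifies the last value for patients whose Period 2 ended because SALT rose above 20. The rule is not limited to them. It also takes in patients whose last Period 2 reading was ≤20 and who have none afterwards: consent withdrawn, lost to follow-up, withdrawn after emergency unblinding (Protocol 9.4), or later visits missed (Protocol 11.2 allows no SALT when a visit cannot be in person because of COVID-19).

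Hair loss after dose reduction or discontinuation takes time to appear. A reading of ≤20 at Period 2 Week 4 says little about Week 24, yet the table would count that patient exactly like one observed at ≤20 at Week 24. The percentages and their intervals are the whole primary result of this descriptive study, and Table 14.2.1.1 goes into the abbreviated report that supports the NDA.

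**Working it through.** **Inputs.** About 50 responders per dose group and about 25 per Period 2 arm (Protocol 13.1); 1:1 re-randomization (Protocol 8.3); six four-weekly SALT visits in Period 2 (Protocol 8.1); 95% Wald interval with continuity correction (SAP 8.2.2). The documents give no dropout rate and no LOM rate, so both are assumed over a range.

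**Step 1: the plan's own figure.** 50 × 1/2 = 25 per arm, as stated. There is no power calculation to reproduce.

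**Step 2: who is affected.**
- LOM patients: the last Period 2 SALT is >20, so they are classified correctly.
- Patients with SALT ≤20 at Week 24: classified correctly.
- Patients who only stop study drug: Protocol 9.3 keeps them in visits and efficacy assessment through the 24-week period, so the rule should not touch them.
- Patients with a Period 2 SALT ≤20 and none later: counted as maintained, though their Week 24 status is unknown.

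Patients with no Period 2 SALT at all are a separate question and are not counted here.

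**Step 3: worst-case bound.** Take an arm of 25 with L observed LOM and k early leavers at ≤20.
- SAP rule: (25 − L)/25.
- Leavers not counted as maintained: (25 − L − k)/25.
- Leavers omitted: (25 − L − k)/(25 − k).

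The first two differ by k/25, or 4.0 points per leaver. The interval is p ± [1.96·√(p(1 − p)/n) + 1/(2n)]. With L = 10 and k = 3:
- SAP rule: 15/25 = 60.0% (38.8 to 81.2).
- Leavers not maintained: 12/25 = 48.0% (26.4 to 69.6).
- Leavers omitted: 12/22 = 54.5% (31.5 to 77.6).

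With 1, 2 or 5 leavers the gap between the first two is 4, 8 or 20 points.

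**Step 4: expected overstatement.** Let S be the true proportion maintaining to Week 24, with a constant LOM probability per visit h = 1 − S^(1/6). Let D be the probability of leaving by the fifth visit in the absence of LOM, unrelated to later outcome, with c = 1 − (1 − D)^(1/5) after each of visits 1 to 5. The SAP rule then reports S(1 − D) plus the proportion who left at ≤20, which is the sum over v = 1 to 5 of (1 − h)^v·(1 − c)^(v − 1)·c.

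For S = 0.50 and D = 0.10: completers 0.50 × 0.90 = 0.450, leavers 0.072, reported 0.522, overstatement 2.2 points.

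If everyone who leaves does so just after Week 4, the overstatement is D·[(1 − h) − S]. For S = 0.50 and D = 0.20 this is 0.20 × (0.891 − 0.500) = 7.8 points.

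| True Week 24 maintenance | Dropout 5 / 10 / 20%, spread over visits | Dropout 5 / 10 / 20%, all just after Week 4 |
|---|---|---|
| 80% | 0.5 / 1.0 / 2.0 points | 0.8 / 1.6 / 3.3 points |
| 50% | 1.1 / 2.2 / 4.5 points | 2.0 / 3.9 / 7.8 points |
| 30% | 1.4 / 2.7 / 5.6 points | 2.6 / 5.2 / 10.4 points |

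Every entry is positive. At equal dropout the overstatement is larger where LOM is more frequent, which narrows the contrast between arms. Under these assumptions a Kaplan-Meier estimate, which censors leavers, is unbiased for S.

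**The case against.** Several points on the other side stand and limit the finding.

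- **The SAP did not clearly overwrite a defined endpoint.** A reader might infer that it did. But Week 24 is tied to this analysis only in the rationale in Protocol 8.4. The sections that define the co-primaries name no week, missing SALT data were left to the SAP, and the SAP has primacy. The texts need aligning.
- **SAP 8.5.1 does not contradict SAP 8.2.1.** Kaplan-Meier censoring applies to every patient without LOM, including those who complete 24 weeks at ≤20, so being censored does not mean not maintained. What remains is that one analysis uses the length of follow-up and the other ignores it.
- **The affected group is narrow.** Patients who only stop drug are still followed, and a missed visit matters only if no later Period 2 SALT exists. The Early Termination Visit includes a SALT, but for someone leaving at Week 6 that is still an early reading.
- **Four points per leaver is a bound.** It compares counting every leaver as maintained with counting none, and some would have maintained. In the Step 3 example the SAP interval, 38.8 to 81.2, covers both alternatives. No test is affected.
- **Much of the information is already planned.** Table 14.2.2.2 gives SALT ≤20 and >20 at each Period 2 visit. With the default header denominator (SAP 4) its Week 24 row for ≤20 would be close to the stricter count. Time to LOM, missing SALT by visit and disposition are also tabulated. None is named as a check on the primary, however, and the by-visit table does not carry earlier LOM forward.

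**Conclusion.** The point holds in a limited form and should be corrected. The last-observed rule is right for patients with LOM. It counts patients with SALT ≤20 and no later Period 2 reading as maintained, which can only leave the Week 24 maintained percentage unchanged or raise it. The worst case is 4 points per such patient in an arm of 25. The expected overstatement is roughly 0.5 to 6 points for 5 to 20% dropout spread over visits, and about 10 points in the extreme case of 20% leaving just after Week 4 with 30% true maintenance.

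These figures rest on assumed dropout and LOM rates, a constant LOM hazard, and dropout unrelated to later outcome. The documents do not support reading the worst-case gap as the bias. The effect is on descriptive estimates and their intervals.

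**What to change.** In SAP 8.2.1:

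1. Define LOM as SALT >20 at any Period 2 visit, and state which score applies. Under SAP 4, patients were moved between parts on SALT rounded to an integer, while analyses use unrounded values. A patient at 20.3 at Week 8 rounds to 20 and stays in Period 2; if at 15 by Week 24, an unrounded any-visit rule calls this LOM and a rounded rule calls it maintained. Use the same choice in SAP 8.5.1.
2. Define maintained as no LOM and SALT ≤20 at Period 2 Week 24 (study Week 48).
3. Show *no LOM, not assessed at Week 24* as a separate row in Table 14.2.1.1, not counted as maintained.
4. Name the Kaplan-Meier estimate of LOM at Week 24 as the supportive analysis that censors these patients. The analysis is planned, but SAP 8.5.1 lists only quantiles and a plot, so the estimate must be added. Say also that LOM found at the Week 24 visit counts as by Week 24: on the target days in SAP Table 2 that visit falls at (337 − 169 + 1)/7 = 24.14 weeks, just past the 24-week censoring cap.
5. Keep the last-observed rule as a sensitivity analysis in SAP 8.2.3.
6. List the change in SAP 13, and align SAP 8.2 and Protocol 13.2.1 with the Week 24 statement in Protocol 8.4.

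The cost is some SAP wording, one table row and one added estimate, with no new data. The maintained percentage may be lower than under the present rule, and it is conservative if leavers stay in the denominator, which is why the Kaplan-Meier figure should stand beside it.
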